6.3 Sample Size

From extensive past experience, the 12-month validated abstinence rate (Primary outcome) associated with UC in our setting is 14% [51]. Our projection of a feasible rate with the EC is based on our work and two published studies. Our recent work [52] suggests that EC delivers nicotine quickly, with T_{max} occurring within 5 minutes. This is similar to nicotine nasal spray. In a comparative study of the nasal spray + patch versus patch alone, 1-year abstinence rates were 27% vs. 11%, RR= 2.45 [53]. More relevant, in a recent cohort study a second generation EC achieved 36% CO validated abstinence at 6-months [54]. Assuming 25% relapse between 6 and 12 months [55], this would translate to a 1-year rate of 27%. Relative to our assumed UC rate, this would give RR = 1.9. However, in deciding an appropriate sample size for this study we have been more conservative. We wish to detect a RR of 1.7 (EC rate = 24%) with 0.95 power, but also have reasonable power (say, 0.75) if the RR should be as low as 1.5 (EC rate = 21%). This latter figure would still represent a clinically significant difference. To achieve these levels of power (2-sided, alpha = 0.05, continuity correction), a total of 886 participants (443 in each group) are required.

If we find no significant difference in abstinence rates between the study arms then we will undertake a non-inferiority analysis. Our sample size of 886 will provide 90% power to exclude a difference in favour of the standard group of more than 5%.

6.4 Statistical Analysis

Analyses will be undertaken after the last participant has completed the 12-month follow-up and the database has been locked.

For the primary analysis the proportion of people remaining abstinent at a year will be compared between the study arms using Chi-squared test with a secondary logistic regression adjusted for study site, sex, age, education, marital status, occupation, entitlement to free prescriptions, ethnicity, daily cigarette consumption, FTCD, age started smoking, partner smoking status, previous smoking cessation medicines used.

For the secondary analyses, we will examine the differences between study arms in the proportions of participants with sustained abstinence at 4, 24 and 52 week follow-up, and sustaining a 50% or greater reduction in baseline cigarette consumption and CO levels at 52 weeks, using Chi-squared test/logistic regression. The frequency of

adverse reactions will also be compared between arms. Between-group differences in urges to smoke and other tobacco withdrawal symptoms will be examined using ANOVA, controlling for baseline ratings. We will also examine time to relapse in a secondary analysis using a Cox analysis with model adequacy assessed by cumulative martingale residuals. An intention to treat analysis will be used with participants lost to follow-up or not providing biochemical validation included as non-abstainers [50]. A sensitivity analysis will be conducted with only participants who attended at least one treatment session from the TQD included.

Economic analyses

The trial will include an incremental cost-effectiveness analysis of EC over and above UC. Intervention and UC costs will be estimated using local costs of staff time, overheads and smoking cessation aids used in each trial arm. Patients will be asked to complete a questionnaire to record their utilisation of smoking cessation materials and services. This will enable a distribution of patient costs to be constructed and secondary analysis of the relationship between patient cost and outcome. The EQ-5D [49] will be completed by patients at baseline, 6 and 12 months with population values attributed to estimate Quality Adjusted Life Years (QALYs). The QALY change will be calculated using the area under the curve method [56]. Patient costs will be combined with QALY changes to estimate the incremental cost per QALY of EC over and above usual care at follow up. The health economic analysis will use existing models to estimate the potential long-term health care cost savings from smokers quitting smoking as a result of the intervention. These will be combined with longer term health utilities from published studies according to smoking status. The combination of trial data and health utility data will provide inputs to a longer term health economic model to estimate the longer term QALYs and cost per QALY gained.

We will construct cost-acceptability curves [56] to demonstrate the probability that EC is more cost-effective than usual care at a range of threshold values for a QALY.

7 Data Handling & Record Keeping

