Study Centre(s)	
 1. Tobacco Dependence Research Unit, Wolfson Institute of Preventive Medicine, QMUL 2. East Sussex Stop Smoking Service (Quit 51) 3. Leicester Stop Smoking Service
Objectives	
Primary: To determine the 12-month sustained biochemically validated abstinence rates in smokers using EC compared to smokers using standard NRT.
 
Secondary: Abstinence rates at 4 weeks and 6 months, CO validated sustained abstinence rates between 6 and 12 months, effects of the two treatments on smoking reduction in participants who did not achieve full abstinence, changes in urges to smoke and other tobacco withdrawal symptoms at 1 and 4 weeks, ratings of the two treatment approaches by patients, rates of adverse reactions associated with the use of EC and NRT, cost-effectiveness of EC compared to NRT.

Number of Subjects/Patients	886 randomised participants
Main Inclusion/Exclusion Criteria	
Inclusion criteria: 18 years and older, current smoker accessing a stop smoking service, able to read/write/understand English.
 
Exclusion criteria: Pregnant or breastfeeding, strong preference to use or not to use NRT or EC in the quit attempt, currently using NRT or EC, already enrolled in interventional research.

Statistical Methodology and Analysis	
Abstinence rates and rates of those sustaining a 50% or greater reduction in baseline cigarette consumption and CO levels will be compared between the study arms using a Pearson Chi-squared test with logistic regression. Frequency of adverse reactions will be compared between arms. Time to relapse will be analysed using a Cox analysis. If no significant difference in abstinence rates is detected between the study arms then a non-inferiority analysis will be undertaken. Participants lost to follow-up or not providing biochemical validation will be included as non-abstainers.

GLOSSARY

AE	Adverse event
AR	Adverse reaction
CO	Carbon monoxide
CPD	Cigarettes per day
DMEC	Data Monitoring and Ethics Committee
EC	Electronic cigarette
EQ5D	European Quality of Life -5 Dimensions
FTND	Fagerstrom Test of Nicotine Dependence
JMRO	Joint Management Research Office
LOR	Letter of recommendation
MPSS	Mood and physical symptoms scale
NRT	Nicotine replacement therapy
QA	Quality assurance
QC	Quality control
RCT	Randomised controlled trial
SAE	Serious adverse event
SAR	Serious adverse reaction
SSC	Study Steering Committee
SSS	Stop Smoking Service

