2.1 Trial Objectives

Primary Objective - To determine the 12-month sustained, biochemically validated abstinence rates in smokers using EC compared to smokers using standard NRT.

Secondary Objectives -

1. Abstinence rates at 4 weeks and 6 months.
2. Abstinence rates between 6 and 12 months
3. Effects of the two treatments on smoking reduction in participants who did not achieve full abstinence.

4. changes in urges to smoke and other tobacco withdrawal symptoms at 1 and 4 weeks.
5. Ratings of the two treatment approaches by patients.
6. Rates of adverse reactions associated with the use of EC compared to standard NRT.
7. Cost-effectiveness of EC compared to standard NRT.

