3.2 Inclusion Criteria

- Aged 18 or over
- Current smoker accessing the SSS
- Able to read/write/understand English

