4.5 Measures

- Demographic details, smoking and medical history
- Fagerstrom Test of Cigarette Dependence (FTND) [47]
- Mood and Physical Symptoms Scale (MPSS): Measure of severity of urges to smoke and other tobacco withdrawal symptoms [48]
- Self-reported smoking status
- End-expired carbon monoxide reading: Collected using a calibrated CO monitor. A reading of <8ppm would be used as a cut-off for abstinence
- Adverse reactions
- Use of EC/NRT and ratings of helpfulness to refrain from smoking and satisfaction in comparison to usual cigarettes. Participants who stop using EC will also be asked their reasons for doing so.
- European Quality of Life-5 Dimensions (EQ5D) questionnaire at baseline and at 6 and 12 months [49]
- Smoking cessation service and health service use at baseline and at 6 and 12 months

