4.8 Schedule of Assessment

Measures/ Procedures	Study session							
	Baseline	TQD	TQD+1 week	TQD+2 weeks	TQD+3 weeks	TQD+4 weeks	TQD+24 weeks	TQD+52 weeks
Informed consent	X							
Baseline questionnaire	X							
Current illness	X		X	X	X	X	X	X
Current medication	X		X	X	X	X	X	X
Randomisation		X						
Commitment form		X						
CO validation	X	X	X	X	X	X		X (if report abstinence or at least 50% reduction)
MPSS	X	X	X			X		
Smoking status/CPD	X	X	X	X	X	X	X	X
Adverse reactions			X	X	X	X	X	X
EC/NRT ratings			X			X		
Quantity/dose of EC/NRT used and helpfulness		X	X	X	X	X	X	X
EC dispensed, demonstration on first use		X		X				
NRT* dispensed, demonstration on first use		X		X		X		
EQ5D questionnaire	X						X	X
Smoking cessation service and health service use	X						X	X

* Dispensing sessions may differ slightly between sites depending on local SSS practices

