6.2 Secondary Endpoints

- CO validated sustained abstinence rates at 4 and 24 weeks post-TQD
- CO validated sustained abstinence rates between 24 and 52 weeks
- 7-day point prevalence abstinence at 4, 24 and 52 weeks
- Smoking reduction in participants who did not achieve full abstinence
- Treatment ratings (e.g. satisfaction, helpfulness)

- Changes in urges to smoke and other tobacco withdrawal symptoms at 1 and 4 weeks.
- Adverse reactions
- Cost-efficacy of the interventions.

Abstinence at 4 weeks after TQD would be defined as a self-report of no smoking of conventional cigarettes (not a puff) for the previous 2 weeks, validated by a CO reading of <8ppm. Participants who do not provide a CO reading at Week 4 will be considered to be smoking. 24 and 52 week sustained abstinence will be calculated in accordance with the Russell Standard [50] as a self-report of smoking no more than 5 cigarettes since 2 weeks post-TQD. This self-report will be validated by CO readings as above for the 52 week follow-up. Participants lost to follow-up or not providing biochemical validation will be included as non-abstainers.

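### The 52-week smoking-reduction rule can score a CO-confirmed non-smoker with a low baseline CO as not reduced, and sections 6.2 and 6.4 differ on who is analysed

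*Protocol*

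**What the plan says.** Reduction is defined in the analysis text. Section 6.4 of the protocol compares the proportions of participants "sustaining a 50% or greater reduction in baseline cigarette consumption and CO levels at 52 weeks", and the statistics row of the synopsis has the same rule: "rates of those sustaining a 50% or greater reduction in baseline cigarette consumption and CO levels will be compared between the study arms". Read naturally, cigarettes and CO must both fall by at least half. Neither place gives another way to satisfy the CO part.

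Abstinence is confirmed by an absolute level. Section 4.5: "A reading of <8ppm would be used as a cut-off for abstinence". Section 6.2 applies the same cut-off at 52 weeks.

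On entry, section 3.2 asks only for a "Current smoker accessing the SSS" who is an adult and can manage English. There is no minimum CO and no minimum daily consumption.

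On who is analysed, section 6.2 lists the endpoint as "Smoking reduction in participants who did not achieve full abstinence", and section 2.1 and the objectives row of the synopsis carry the same limit. Section 6.4 and the statistics row of the synopsis do not. Full abstinence is not defined. Sustained abstinence at 24 and 52 weeks is defined, "as a self-report of smoking no more than 5 cigarettes since 2 weeks post-TQD", and 7-day point-prevalence abstinence at 52 weeks is a separate endpoint.

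On who gives a CO reading at week 52, section 4.8 has "X (if report abstinence or at least 50% reduction", and section 4.4 agrees.

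**The concern.** One CO test is relative to baseline and the other is absolute. When baseline CO is low, half of it lies below the abstinence cut-off. A week-52 reading between the two values then passes as non-smoking and fails as reduced. A person whose cigarette consumption has fallen by 100%, and whose CO meets the trial's own standard for not smoking, is counted with those who did not cut down.

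The misclassification is systematic, since it can fall only on people who enter with low CO. At stake is the meaning of one secondary endpoint and, because 6.2 and 6.4 name different populations, its denominator.

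**Working it through.** **The plan's own figure.** The protocol states no figure for the reduction endpoint. Its sample size concerns the primary endpoint and reproduces closely. For 14% vs 21%, two-sided alpha 0.05 and power 0.75, the uncorrected size is 409 per arm. The continuity correction n/4 × [1 + √(1 + 4/(n × 0.07))]² raises this to 437, against 443 planned. With 443 per arm and the correction, power is 0.757 at 21% and 0.955 at 23.8% (1.7 × 14%). The reduction rule does not enter this calculation.

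**Where the two CO tests disagree.** Let b be baseline CO and f the week-52 CO.

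- Abstinence test (4.5): f < 8.
- CO part of the reduction test (6.4): f ≤ b/2.
- A reading passes the first and fails the second when b/2 < f < 8, which requires b < 16.
- In whole ppm the largest passing f is 7, and 7 > b/2 requires b < 14, so b is 13 or lower.

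| Week-52 CO (ppm) | Fails the halving rule if baseline CO is |
|---|---|
| 7 | below 14 |
| 6 | below 12 |
| 5 | below 10 |
| 4 | below 8 |

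With a baseline of 14 ppm or more, every whole-ppm reading below 8 passes both tests.

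**Two examples.** Baseline 10, week-52 CO 6: fall = (10 − 6)/10 = 40%, so not reduced, although 6 < 8. Baseline 12, week-52 CO 7: fall = (12 − 7)/12 = 41.7%, again not reduced, although 7 < 8.

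**Who can be such a case.**

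1. If 6.4 carries the limit in 6.2, and full abstinence means sustained abstinence: people who smoked more than five cigarettes after week 2 but have stopped by week 52. They report abstinence, so 4.4 and 4.8 ask them for a CO reading.
2. If 6.4 is read without the limit: sustained abstainers as well.
3. If full abstinence also covers CO-confirmed 7-day abstinence at week 52: almost nobody.

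**How often.** The protocol gives no CO distribution, so this is assumption throughout. Baseline CO was taken as lognormal, rounded to whole ppm, and CO in non-smokers as Poisson, with 400,000 draws per cell. Each entry is the share of those reading below 8 ppm whose week-52 CO exceeds half of baseline.

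| Baseline mean (SD), ppm | Share with baseline below 14 | Non-smoker mean CO 2 | 3 | 4 |
|---|---|---|---|---|
| 15 (7) | about 49% | 2.6% | 7.1% | 12.7% |
| 20 (9) | about 24% | 0.7% | 2.3% | 4.6% |
| 25 (10) | about 8% | 0.1% | 0.5% | 1.1% |

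The range is about 0.1% to 13%. A second set of assumptions (lognormal median 14 to 24 ppm, log-SD 0.5 to 0.6, non-smoker mean 2.3 to 3.1 ppm) gave 0.6% to 11%, inside that range.

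**The case against.** The two rules serve different endpoints: the absolute cut-off validates abstinence, and the 50% fall supports a claim of having cut down. That is correct, so this is incoherent scoring across endpoints and not a flat contradiction.

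Two readings weaken the point. If full abstinence includes point-prevalence abstinence at week 52, the affected people leave the analysis. If cigarettes and CO are two separate outcomes, the cigarette outcome is scored correctly, though the CO outcome still fails. The protocol states neither reading.

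It can also be said that such detail belongs in the SAP. But the protocol itself fixes the 50% CO criterion, so the matter is how a stated rule works and not a missing detail. The objection that the frequency may be close to zero stands; the lower end of the range is 0.1%.

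A reader might go further and infer that the rule strips out primary-endpoint successes and so shrinks the advantage of EC. At the planned 24% and 14% of 443 per arm there would be about 106 and 62 validated abstainers, and a 5% failure rate would remove about 5 and 3. The documents do not support this as the main case. Those people are sustained abstainers, whom 2.1 and 6.2 place outside the outcome. For late or repeat quitters the protocol gives no rates by arm, so neither the direction nor the size of any bias can be derived. Even with everyone included, an equal 5% loss would move the abstainers' contribution only from 24% − 14% = 10 points to 22.8% − 13.3% = 9.5 points and leave their ratio at about 1.7.

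**Conclusion.** The defect is real but narrow. On the natural reading that both falls are required, a participant with a baseline CO of 13 ppm or lower who reports no smoking and reads below 8 ppm at week 52 can be scored as not reduced. With the limit in 6.2 applied, and full abstinence taken to mean sustained abstinence, the cases are late or repeat quitters. Sustained abstainers are affected only if 6.4 is read without that limit.

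The frequency, about 0.1% to 13% of CO-confirmed non-smokers, rests wholly on assumed CO distributions. No direction of effect on the arm difference is established. Only this secondary endpoint is affected. The change is still worth making, because it corrects a rule that the protocol itself states and costs almost nothing.

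**What to change.** In section 6.4, and to match in the statistics row of the synopsis:

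- Repeat the population from 6.2 and define it: participants without CO-validated sustained abstinence at 52 weeks.
- State that, within this population, a participant who reports no smoking and has a CO below 8 ppm at week 52 meets the reduction endpoint.
- Apply the 50% fall in CO only to participants still smoking at week 52.

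The cost is two or three sentences. The readings are already scheduled in 4.4 and 4.8, and nothing changes in the primary analysis or the sample size.

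There is a small downside. For someone with a very low baseline CO, a reading below 8 ppm confirms little: 7 ppm at entry and 7 ppm at week 52 would count as reduced with no change in CO. The trial's abstinence endpoints already accept the same reading, so the fix adds no new weakness of principle, but the limitation should be acknowledged.

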7.1 Confidentiality

Only study personnel will have access to study data. We will not request any patient identifiable data or medical information about participants from their other doctors (hospital or general practitioner, GP).

The Participants' GPs will be advised of their participation in the study, providing the participant gives consent to this. If the participant does not wish their GP to be informed, this will not prevent them from taking part in the study.

All information will be kept confidential, as per normal practice for patients attending the SSS. Copies of all documents regarding the study will be kept in the trial master file (TMF) and/or relevant site file. Participants will be assigned a trial ID number.

7.2 Study Documents

- A signed protocol and any subsequent amendments
- Current/Superseded Patient Information Sheets (as applicable)
- Current/Superseded Consent Forms (as applicable)
- Indemnity documentation from sponsor
- Conditions of Sponsorship from sponsor
- Conditional/Final R&D Approval
- Ethics submissions/approvals/correspondence
- CVs of CI and site staff
- GCP certificates of study and site staff
- Delegation log
- Patient identification log
- Screening log
- Enrolment log
- Correspondence relating to the trial

7.3 Case Report Form

Appropriately trained staff will be responsible for ensuring the correct sections are completed at the relevant time-points throughout the study. All completed CRFs will be reviewed and signed off by the PI.

7.4 Record Retention and Archiving

All information relevant to the study will be archived and retained for 20 years at the Barts Health NHS Trust facility in [name]. Local site files will be archived according to local procedures, for a minimum of 20 years. Electronic data (which will not include participants' personal data) will be kept on a Barts' CTU secure online database for 20 years, following the CTUs SOP on electronic archiving. Sponsor will be informed in writing when and where all data is archived.

7.5 Compliance

The CI and Site PIs will ensure that the trial is conducted in compliance with the principles of the Declaration of Helsinki (1996), and in accordance with all applicable regulatory requirements including but not limited to the Research Governance Framework, sponsor's policies and procedures and any subsequent amendments.

7.6 Clinical Governance Issues

7.6.1 Ethical Considerations

This protocol and any subsequent amendments, along with any accompanying material provided to the patient in addition to any advertising material will be submitted by the Chief Investigator to a Research Ethics Committee.

7.7 Quality Control and Quality Assurance

7.7.1 Summary Monitoring Plan

This study will be subject to the Quality Control (QC)/Quality Assurance (QA) system of the Joint BH/QMUL Research Management Office (JRMO).

Monitoring will be proportional to the objective, scope, design, size, complexity and risks of the project. The JRMO will risk assess the trial in line with the JRMO risk assessment standard operating procedure. The trial's risk assessment will assist the JRMO in the trial's final monitoring design format and schedule. The monitoring design will be detailed in the final monitoring plan and signed by the CI. A Copy of the plan will be kept in the TMF. The CI will ensure that this agreement/wording is not altered without written authorisation (email confirmation) from the JRMO; all new versions will be signed. The study manager will monitor the host sites using the same monitoring design and frequency as for the main site.

CI/study team will notify the GCP team once the first patient has been consented onto the trial at each site. The JRMO will update the monitoring schedule with the date the first monitoring event is due.

7.8 Audit and inspection

The investigator will permit study-related monitoring, audits, and inspections by the Ethics Committee, the sponsor, Barts CTU, government regulatory bodies of all study related documents (e.g. source documents, regulatory documents, data collection instruments, study data etc.).

7.9 Reporting of Serious breaches in GCP or trial protocol

All breaches and potential breaches in GCP or trial protocol will be logged by the coordinating office and reported to the Sponsor and Barts CTU within 24 hours. Any breach deemed serious by the sponsor will be reported to the REC within 7 days as per the REC procedure.

7.10 Trial Committees

A Study Steering Committee (SSC) and Data Monitoring and Ethics Committee (DMEC) will be convened. A trial management committee (TMC) will also be convened. The TMC will consist of [name] (chief investigator), [name] [name] (study manager), [name] (researcher), [name] (co-investigator) and an appropriate member of the Barts CTU.

